Aim 3. Risk of PTD & LBW for untreated depression (Cohort D vs. E)

Cox proportional hazards regression will be used to obtain point and interval estimates of the hazard ratio for PTD associated with untreated depression, vs. no depression, with adjustment for potential confounders, as described above. Parameter estimation, the approach to inclusion of potential confounders and model diagnostics are as described above for Aim 1 analyses.

To evaluate potential dose-response relationships, we will examine the strength of the association between PTD and severity of depressive symptoms. Severity will be based on results of the KPNC universal screening and clinical diagnosis of depression from the KPNC EMR. Those with a clinical diagnosis of depression will be considered to be the most severe cases followed by those who screened positive with PHQ-9 higher scores (e.g., > 20). Those who screened positive, but with lower PHQ-9 scores (10-19) will be considered to have moderate depression. The effect of severity will also be examined in terms of duration.

Analyses of LBW as the outcome will parallel those described above for PTD, but logistic regression techniques will be used rather than the Cox model.

Aim 4. Difference in treatment effectiveness by depression type (with and without comorbidity)

Analyses of Aims 1, 2 and 3, will be initially stratified by depression type, with or without other psychiatric comorbidity (yes/no). Heterogeneity in treatment effectiveness by depression type will be assessed by inclusion of appropriate cross-product (interaction) terms in regression models outlined above, using a likelihood ratio test. If there is evidence of heterogeneity, point and interval estimates of relative hazards/odds ratios of interest by comorbidity status (yes/no), adjusted for confounders, will be obtained via linear combination of regression parameter estimates (main effect and interaction terms, as appropriate).

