6.2.2 Sample size and statistical power

We expect to measure primary exposures (depression and treatment), and outcomes of interest (PTD, LBW) in approximately 88,000 women (stage-one sample). Randomly sampling from the stage-one cohort, we expect to recruit 400 pregnant women from each cohort (see Figure 2). Given the lack of methods for power calculations for the semiparametric maximum likelihood estimator (SMLE) in our two-stage sampling scheme, we very conservatively present minimum detectable effect calculations assuming the second stage sample of 3,600, noting that the gains in precision and statistical power in utilizing the measurements in stage-one sample of 88,000 women will be significant. In a small simulation study described below, we examine efficiency gains of an ad-hoc two-stage relative hazard estimator currently under investigation, which is an alternative to the semiparametric maximum likelihood estimator, attractive in its simplicity. These results provide information on the efficiency gains that can be expected in our two-stage design with the maximum likelihood estimation; the maximum likelihood estimator will be more efficient than the ad-hoc. Given results of the preliminary simulation study, we also present below estimates of minimum detectable effects using the two-stage SMLE for most estimates (in brackets, assumptions described below). Power calculations are based on the likelihood ratio test in the context of a Cox proportional hazards regression analysis and a logistic regression analyses, as appropriate to the outcome^{89 90}.

Given previous experience^{3,91-93}, we expect negligible loss to follow-up (< 1%). Based on our experience with our study population⁹⁴, we expect a rate of PTD (gestational age < 37 weeks) ranging from 8% - 11% and LBW ranging from 5% to 10%.

Each primary contrast of interest in analyses addressing **Aims 1 through 3** can be characterized as a comparison of two groups of 400 women with respect to risk of study outcomes of interest (N=800). Minimum detectable hazard ratios for PTD range from 1.69 – 1.83 across the range in expected rate of PTD (Table 5). Minimum detectable odds ratios for LBW range from 1.67 to 2.05 across the range in expected event rate.

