Relevant to **Aim 4** analyses of heterogeneity in the association between treatment/depression and PTD by psychiatric comorbidity status (yes/no with 50% of total stage 2 sample in each of the two groups), the minimum detectable hazard ratio for effect modification (interaction) was calculated, assuming a pairwise comparison of treatment effect (e.g. A vs. D) and the midpoint of the range in expected PTD rate (9.5%) [N for analyses = 1600]. The hazard ratio for effect modification is interpreted as the factor by which exposure to the effect modifier (comorbidity status = yes) increases the hazard ratio associated with treatment, over and above that in those unexposed to the effect modifier (comorbidity status = no). Using methods as outlined above, the minimum detectable hazard ratio for effect modification is 1.50, and similarly for analyses of LBW, the minimum detectable odds ratio for effect modification is 1.62 (two-sided test, $\alpha=.05$, power =.80). While this stratification analysis is an *a priori* aim of the study with relevant clinical implications, we will be conservative in interpretation of our findings due to increased number of comparisons from stratification by depression type, though the need to adjust for multiple comparisons remains controversial⁹⁵⁻⁹⁷.

Table 4. Comparison of Maternal Age and Race/Ethnicity for Newborns between KPNC and the General Population in the KPNC Service Regions

Characteristics	KPNC Births (%)	All births in the KPNC Service Regions (%)
Maternal age		
< 20	12	10
20-29	43	52
30+	45	38
Maternal race/ethnicity		
Asian	15	16
Black	10	10

Table 5. Minimum detectable hazard ratios (HR) for preterm delivery and minimum detectable odds ratios (OR) for low birthweight in a pair-wise comparison of depression exposure/treatment categories (N=800); two-sided test, significance level (α) = .05, power (1- β) =.80.

Preterm Delivery (HR)		Low Birthweight	
Rate = 8%	Rate = 11%	Rate = 5%	Rate = 10%

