Efficiency increase resulting from two-stage study design: A preliminary simulation study has been conducted providing information on the expected efficiency gains of the two-stage SMLE, relative to an analysis of the stage-two subsample only. For our preliminary simulation study, we made a few simplifying assumptions. We assumed three depression status categories, none, depressed without treatment, depression with treatments, with population prevalence set at 70%, 25% and 5%, and outcome relative risks of 1.0 (ref), 2.0 and 3.0, respectively. We assumed one binary confounder with varying prevalence across depression categories and strength of association with outcome. The event incidence was assumed at 5% (among those unexposed to depression and confounder). The stage-one sample size was 88,000, with random selection of 400 in each of the three exposure categories. Across the scenarios considered relative efficiencies [i.e. Var(stage 2

MLE) / Var(SMLE)] ranged from 4 to 82, demonstrating substantial gains by utilizing exposure and outcome information in the full sample of 88,000.

As a very crude approximation to the impact of incorporating the exposure and outcome information on 88,000 women, we took an “effective sample size” approach, and assumed the worst case among the simulation scenarios considered, where the relative efficiency of the SMLE was approximately 4.0. Thus, rather than basing power calculations on the stage-two sample size of 800, we based them on 3200 (i.e. $4.0 * 800$; 1,600 in each cohort category). Under these assumptions, the minimum detectable PTD hazard ratios are significantly decreased, ranging from 1.32 to 1.38 (for PTD rate ranging from 8%-11%) in pair-wise comparisons of depression exposure/treatment categories of interest. Similarly, the minimum detectable LBW odds ratios range from 1.32 to 1.45 (for LBW rate ranging from 5% to 10%). In addition, taking the same approach to estimation of efficiency gains, the minimum detectable hazard ratio and odds ratio for effect modification by comorbidity status (yes vs. no) are 1.31 and 1.37 in analyses of PTD and LBW, respectively. We acknowledge that these estimates of gains in efficiency are based on results from a simulation study which did not reflect the complexities in analyses that this study will encounter (e.g. multiple confounders, both multicategory and continuous).

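### The Aim 4 minimum detectable effects do not follow from the plan's stated inputs, and the pairwise LBW odds ratios are also understated

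*Combined protocol and SAP*

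**What the plan says.** All the power figures are in section 6.2.2, at two-sided 0.05 and 80% power.

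- **Pairwise contrasts, stage two (400 vs 400).** "Minimum detectable hazard ratios for PTD range from 1.69" to 1.83 for PTD rates of 11% down to 8%. For LBW at rates of 5–10%: "Minimum detectable odds ratios for LBW range from 1.67 to 2.05 across the range in expected event rate".
- **Aim 4 interaction, stage two.** The target is the factor by which comorbidity multiplies the treatment hazard ratio. Comorbidity is split 50/50, and the inputs are "the midpoint of the range in expected PTD rate (9.5%) [N for analyses = 1600", that is, four cells of 400. The result is that "the minimum detectable hazard ratio for effect modification is 1.50, and similarly for analyses of LBW" the odds ratio is 1.62. No main effects are given, and no LBW rate is given for this calculation.
- **Two-stage values.** The plan takes a relative efficiency of 4.0: "rather than basing power calculations on the stage-two sample size of 800, we based them on 3200". The pairwise PTD range becomes 1.32–1.38, and "the minimum detectable LBW odds ratios range from 1.32 to 1.45". By the same approach, "the minimum detectable hazard ratio and odds ratio for effect modification by comorbidity status (yes vs. no) are 1.31 and 1.37" for PTD and LBW.

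Section 6.1, Aim 4, tests heterogeneity with a likelihood ratio test on the interaction terms. It makes the next step depend on that test: "If there is evidence of heterogeneity, point and interval estimates of relative hazards/odds ratios of interest by comorbidity status (yes/no". Those stratum figures come from the fitted interaction model.

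**The concern.** An interaction is a ratio of two stratum-specific effects, so its log variance is the sum of the two stratum variances. With comparable strata it must be harder to detect than the effect in either stratum. The plan says the reverse. One 400-vs-400 contrast needs a hazard ratio of 1.69–1.83, yet the ratio of two such contrasts is said to need only 1.50. The same inversion appears in the two-stage figures, where 1.31 lies below the pairwise range of 1.32–1.38.

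Aim 4 is a numbered aim, and the interaction test decides whether the interaction-model estimates by comorbidity status are produced. If its power is far below 80%, a non-significant result says little. A reader who trusts the stated power could take it as evidence that treatment works equally well in both depression types.

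**Working it through.** **Constants.** z = 1.960 + 0.842 = 2.802. The variance of the log ratio needed for 80% power is (ln effect / z)²:

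- 1.50: 0.0209
- 1.62: 0.0297
- 1.31: 0.00929
- 1.37: 0.0126

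**Step 1: reproduce the plan's pairwise PTD figures.** Take the stated rate r as the reference-group rate, events per group as n(1−(1−r)^HR), and variance as 4/(total events).

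- n = 400: HR 1.685 (11%) and 1.816 (8%), against the stated 1.69 and 1.83.
- n = 1,600: HR 1.321 and 1.380, against the stated 1.32 and 1.38.

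The pairwise PTD figures are sound, and this method matches the plan's.

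**Step 2: bounds for Aim 4, stage two, that need no main-effect assumption.**

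- *From the plan's own pairwise range.* Two equal stratum variances multiply the log effect by √2: 1.69^√2 = 2.10 and 1.83^√2 = 2.35.
- *HR 1.50.* The reference cell has 400 × 0.095 = 38 events and contributes 1/38 = 0.0263. That already exceeds 0.0209 before the other three cells are counted.
- *If 9.5% is the overall rate.* Total events are 1,600 × 0.095 = 152. The variance is at least 16/152 = 0.105, so HR is at least exp(2.802 × √0.105) = 2.48. Detecting 1.50 would need 16/0.0209, about 764 events.
- *OR 1.62.* Each cell contributes 1/(400pq), and pq cannot exceed 0.25. The minimum over four cells is 4/(400 × 0.25) = 0.040, so OR is at least exp(2.802 × 0.2) = 1.75 at any event rate.

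**Step 3: bounds for Aim 4, two-stage, at efficiency 4.0 (1,600 per cell).**

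- *HR 1.31.* The reference cell has 152 events. The remainder is 0.00929 − 1/152 = 0.00271, so each of the other three cells needs 3/0.00271, about 1,107 of 1,600 preterm (69%). If 9.5% is overall, HR is at least exp(2.802 × √(16/608)) = 1.58.
- *OR 1.37.* The minimum is 1/(1600pq) + 3/(1600 × 0.25), which is 0.0207 at a reference-cell rate of 5%, 0.0165 at 7.5% and 0.0144 at 10%. All exceed 0.0126.

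**Step 4: recomputed detectable effects.** Assumptions not in the plan: 9.5% is the reference-cell PTD rate; the reference-cell LBW rate is 5–10%; main effects are as shown. The variance is the sum over four cells of 1/events (Cox) or 1/(npq) (logistic). Power is Φ(ln effect/√variance − 1.96).

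| Cell size | Treatment, comorbidity effect | HR | Power at stated HR | OR at LBW 5% / 7.5% / 10% |
|---|---|---|---|---|
| 400 | 1, 1 | 2.33 | 26% | 3.26 / 2.69 / 2.41 |
| 400 | 2, 2 | 1.97 | 38% | 2.66 / 2.29 / 2.11 |
| 400 | 0.6, 1 | 2.57 | 21% | 3.68 / 2.97 / 2.62 |
| 400 | 0.6, 2 | 2.35 | 25% | 3.32 / 2.73 / 2.43 |
| 1,600 | 1, 1 | 1.54 | 40% | 1.84 / 1.66 / 1.57 |
| 1,600 | 2, 2 | 1.41 | 60% | 1.64 / 1.52 / 1.46 |
| 1,600 | 0.6, 1 | 1.63 | 32% | 1.97 / 1.76 / 1.65 |
| 1,600 | 0.6, 2 | 1.55 | 40% | 1.85 / 1.67 / 1.57 |

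Power at OR 1.62 is about 16–44%, and at OR 1.37 about 24–65%. Simulation with exponential times agrees: 25%, 39% and 21–26% at HR 1.50 (main effects 1, main effects 2, treatment 0.6), and 40%, 59% and 31–39% at HR 1.31.

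**Step 5: consistency of the stated pairs.** An efficiency of 4 roughly halves the log ratio, so 1.50 would become about 1.22 and 1.62 about 1.27. The stated 1.31 and 1.37 imply an efficiency of only (ln 1.50/ln 1.31)² = 2.25 and (ln 1.62/ln 1.37)² = 2.35.

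**Step 6: pairwise LBW.** Likelihood ratio calculation, with the rate taken as the reference-group rate:

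| n per group | LBW rate | Stated OR | Recomputed OR | Power at stated OR |
|---|---|---|---|---|
| 400 | 10% | 1.67 | 1.81 | 67% |
| 400 | 5% | 2.05 | 2.16 | 73% |
| 1,600 | 10% | 1.32 | 1.37 | 70% |
| 1,600 | 5% | 1.45 | 1.51 | 70% |

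**Possible origin.** The values 1.50 and 1.62 match detectable main effects for 800 vs 800 (1.505 at PTD 9.5%, 1.62 at LBW 7.5%). This is inferred from the match. The conclusion does not depend on it.

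**The case against.** The stage-two bounds in step 2 leave little to argue, but four points deserve an answer.

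- **The two-stage hazard ratio is not strictly impossible.** This stands. HR 1.31 could arise with about 69% preterm in three cells, or at an efficiency of about 6.5–14 over the main effects above. The plan's simulations ranged from 4 to 82 and 4.0 was their worst case, so real power may be better than 31–60%. But the plan says it used 4.0, and the simulation it describes had three exposure categories and one confounder, with no interaction mentioned. Calling the efficiency gain a crude approximation does not help the stage-two figures, which do not use it.
- **The method is partly documented.** Section 6.2.2 names the likelihood ratio test and cites a method paper and a software manual. What is missing is the main effects and the Aim 4 LBW rate. No choice of either rescues the stage-two values.
- **The pairwise LBW figures may be mislabelled risk ratios.** At 400 per group the detectable risk ratios are about 1.67 and 2.04, close to the stated values. At 1,600 per group they are about 1.32 and 1.48, which does not match the stated 1.45. Relabelling alone would therefore not settle it, and this part is modest in any case.
- **Stratified analyses run regardless, and the plan promises cautious interpretation.** Aims 1–3 are indeed analysed within each depression type, but that does not test the difference between types. The promised caution concerns multiple comparisons, that is, false positives. The problem here is low power.

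**Conclusion.** The concern holds. The stage-two Aim 4 values (HR 1.50, OR 1.62) are incompatible with the stated inputs whatever the main effects, and for the odds ratio whatever the LBW rate. At the stated efficiency of 4.0, OR 1.37 is out of reach for LBW rates of 5–10%, and HR 1.31 requires implausible event rates.

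The detectable hazard ratio is about 2.0–2.6 on stage two and 1.4–1.6 two-stage, against the stated 1.50 and 1.31. These ranges assume main effects of 1.0 to 2.0, or a protective treatment at 0.6 with a comorbidity effect of 1–2, and 9.5% as the reference-cell rate. Reading 9.5% as the overall rate puts the minimum at 2.48 and 1.58. The two-stage power loss is conditional on efficiency 4.0.

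The pairwise LBW error is separate and smaller: 67–73% power against 80%. The pairwise PTD hazard ratios reproduce and need no change.

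**What to change.** - Recalculate the Aim 4 detectable effects from the four-cell interaction variance. State the assumed main effects, the LBW rate, and whether each rate applies to the reference cell or overall.
- Give stage-two and two-stage values separately. If an efficiency other than 4.0 is used for the interaction, state and justify it.
- Restate the pairwise LBW odds ratios: about 1.81–2.16 at 400 per group and 1.37–1.51 at 1,600 per group on the stated inputs.
- In section 6.1, Aim 4, commit to reporting the ratio of stratum effects with its confidence interval whatever the likelihood ratio test shows, so that a non-significant test is not read as equal effectiveness.

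The cost is text only. Sampling, models and eligibility are unchanged; the stated figures become less favourable.

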7 STUDY ADMINISTRATION

7.1 Data Collection and Management

7.1.1 Data sources

KPNC EMRs and other clinical databases will be used to identify all women who meet our recruitment criteria and to include them in the study. Approximately 88,000 pregnant KPNC members who are 18 years or older, will be identified and recruited to the study. All eligible pregnant women will be classified into one of the categories based on the diagnosis and treatment of their depression during pregnancy. For each of these nine categories, 400 women (for a total of 3,600) will be randomly selected and recruited to conduct telephone interviews to collect information on confounders and effect modifiers.

Birth outcomes for all participants will be ascertained through the KPNC EMR and other clinical databases

7.2 Confidentiality

All standard procedures following HIPAA requirements will be implemented for this study. Names and other identifying information on study subjects will be obtained for record-keeping purposes only, and no individuals will be identified in any reports from this study. Only persons directly involved in the study will have access to data identifying individual subjects. Records and forms with identifying information will be kept in locked drawers when not in use. Access to computerized information will require simultaneous knowledge of the database, language, file names, and multiple passwords.

7.3 Risks and Benefits

7.3.1 Potential and anticipated risks to research participants.

For participants in the telephone interview (stage-two study), the risk of participating in this study is minimal. Women who had adverse pregnancy outcomes in the past may become

upset when recalling these events. All interviewers will be trained on how to appropriately handle these situations in case they arise. Our experience also indicates that some women find it therapeutic to discuss these events.

7.3.2 Risk Minimization

No invasive procedures are involved in the study protocol, only interviews. All interviewers have had experience interviewing pregnant women and are specifically trained for these types of studies. All of the women contacted for a telephone interview will have received a letter informing them about the study.

7.3.3 Benefits to participants and to society

No direct benefit is expected to participants resulting from participation in the study. Findings from the study in a publishable format will be made available to all participants who request them. The potential benefit to society is to enhance the understanding of the risk-benefit profiles of various treatment options depression during pregnancy to prevent preterm delivery and low birthweight. Because of the prevalence of depression among pregnant women, findings from the proposed study will have a significant public health impact. Correct treatment choices may lead to reduction of PTD and LBW which remain top public health challenges globally.

7.3.4 How potential risks are justified by potential benefits

There is only minimal risk to participants. Potential benefits to society described above can be significant.

7.4 Recruitment Strategy

The chiefs and other obstetricians in the departments of Obstetrics and Gynecology at participating KPNC facilities will be informed of the nature of the study and permission to contact their patients (if selected) in stage-two will be obtained from those departments. Informational posters will be sent to all OBGYN departments for display and OBGYNs will inform all pregnant women about our study during their prenatal visits. For stage-two samples, after they are identified, a letter explaining the study and requesting their participation will be sent to women. A postage-paid and self-addressed refusal card will be included in the letter for participants who choose to refuse. For those who do not return refusal postcards, interviewers will contact women to answer their questions and ascertain their willingness to participate in the study.

7.5 Informed Consent and HIPAA Authorization

7.5.1 Waiver of Consent for Stage-One Sample

A waiver of consent has been granted for the stage-one sample, since the stage-one sample involves data only, there are no risks associated with recruiting subjects, although there is always a small chance of the loss of confidentiality during data analyses. Since there is no direct contact of patients, we do not anticipate an adverse effect on their rights or welfare.

7.5.2 Waiver of Consent for Stage-Two Sample

A waiver of the requirement for participants to sign a written consent form has been granted for the stage-two telephone interviews. As has been used in other studies of telephone interviews, for those who will be contacted by telephone for an interview, the consent process will be conducted over the phone. Verbal Informed consent will be obtained before each interview and no interviews will be conducted without consent for participation. Interviewers who are employees of Division of Research and who have had extensive experience conducting such interviews will obtain the consent. There is no more than minimal risk to participants and there are no other procedures involved beyond an interview.

7.5.3 Waiver of HIPAA Authorization

A waiver of HIPAA Authorization has been granted for both stages of the study.

The stage-one sample will be data only. There will be no direct contact with participants. For the stage-one sample of 88,000 women, we will need to access PHI to identify maternal pregnancy and depression status. The medical record number will be used to link the mother-infant pairs and other datasets on pregnancy, maternal, and birth outcomes. Stage-two will involve telephone interviews for which we are requesting a waiver of written consent for participation (verbal consent will be obtained).

Data with identifiable information will be password protected by the programmer. An additional dataset will be created and used by the programmer which will not include any PHI. Data will not be shared outside of KPNC.

No PHI data will be disclosed to outside investigators. We will provide assurance of the confidentiality and proper procedures for protecting PHI as set forth by the KPNC IRB.

Personal identifiers will be destroyed at the end of study according to IRB requirements.

